Role of FDG-PET CT in the Management of Muscle Invasive Bladder Cancer
NCT04053101
ID: IB2018-TEP vessie
Jan 5, 2017

INTRODUCTION

Bladder cancer is the second urologic cancer in terms of incidence. The prognosis of MIBC is poor, with a 5-year survival rate from 45 to 50% (1). Main prognostic factors are the quality of the surgery (with a complete resection R0), a pelvic LN dissection with at least 10 LN and a pathological Complete Response (pCR) after neoadjuvant chemotherapy (NAC) (2,3). Treatment decisions are taken during a tumor board, based on the staging of local disease, LN status and distant localization.

Usually, CT and less frequently Magnetic Resonance Imaging (MRI) are recommended for LN and metastatic staging of MIBC. For LN staging, CT is used, despite a low reported sensitivity, around 30-53%, but a high specificity between 68 to 100% (6,7). MRI is more accurate for LN staging, mostly by using DWI sequences (sensitivity of 56% and specificity of 94%) (8). FDG-PET CT combines anatomical and metabolic imaging. The sensitivity is usually better for detecting pathological infra centimetric LN, but the specificity is low. In cases of MIBC, several studies have evaluated FDG-PET CT as imaging for initial nodal staging before cystectomy and reported a sensitivity between 29% and 81% and a specificity between 86.7% and 97%, depending on interpretation criteria (9-12). Two meta-analysis evaluated the accuracy of FDG-PET CT in MIBC. The first one found a sensitivity of 57% and a specificity of 92% for preoperative LN staging of MIBC by using FDG-PET CT (13). The second one published in 2018 compared accuracy of CT, MRI and FDG-PET CT for staging bladder cancer (14). MRI and FDG-PET CT had a higher sensitivity (respectively 60% and 56%) compared to CT (40%) while the specificity of all modalities was similar. Other studies evaluated the rate of treatment modification based on the results of FDG-PET CT, around 25% (from 13.5% to 68%) mainly due to the confirmation of metastatic spread (9,15-18). FDG-PET CT has also been indicated to evaluate therapeutic response after chemotherapy (19,20).

To date, FDG-PET CT is not recommended for the staging of MIBC, as a standard of care but rather as an option (21). We aimed to investigate the role of FDG-PET CT and its accuracy in LN staging of MIBC at diagnosis and how it may improve treatment decision.

Patients and Methods

Patients will be retrospectively included from both the University Hospital and the Cancer Center from Bordeaux. To be included in the study, patients should have undergone a FDG-PET CT at the time of diagnosis of MIBC. Only patients with diagnosis of predominant urothelial carcinoma, \geq pT2 of the bladder will be included.

Clinical data collected: center of reference, date of birth, history of tobacco intoxication, performance status, date of relapse and site of relapse, date of the latest news or date of death and status (alive or dead).

Pathological information (which is the gold standard) included biopsy site, date of biopsy, histology, pathological result of cystectomy and LN dissection (TNM classification, status R, number of LN resected, number of positive LN, necrosis, and presence of pCR after NAC). CT data will be extracted from radiological or medical reports (before and after NAC) and the lesions described will be classified according to the 8th TNM classification, actualized in 2017 (22). RECIST1.1 criteria allowed to describe pathological LN (corresponding to LN with smallest axis greater than 15mm). For metastatic lesion, patients will be classified as “M0” (without metastasis), without suspect ¹⁸FDG intake, or as “M1a” in case of metabolic activity of non-regional LN, and as “M1b” in case of distant metastatic lesions. FDG-PET CT results will be extracted from nuclear medicine reports for the University Hospital, or by exam reviewing for Institute Bergonie exams. Data collected were: size, SUV max, Tumor Lesion Glycolysis for each lesion (tumor, LN or metastasis) and TNM staging. If patients undergo a FDG-PET CT before and after NAC, a metabolic response (such as complete, partial, stable, progressive or dissociated) will be notified. Treatment characteristics will be extracted from the database (chemotherapy regimen, type of surgery (Table 1) and radiotherapy modalities).

Objectives

Objective of this study is to evaluate the performance accuracy of FDG-PET CT for LN staging at the diagnosis of MIBC (before and after NAC and before cystectomy and LN dissection).

Statistical analysis

Qualitative values will be described by total numbers and percentage. Quantitative values will be presented as median, minimum and maximum value, average and standard deviation. For diagnosis accuracy of CT and FDG-PET CT, we will calculate the sensitivity, specificity, false positive rate, false negative rate, Youden index.

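### No analysis set is defined for nodal accuracy: entry needs a PET but no nodal pathology, and some pathology follows NAC, so pooled raw figures may not describe accuracy at diagnosis

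*Combined protocol and SAP*

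**What the plan says.** Patients and Methods sets two entry conditions. First, "patients should have undergone a FDG-PET CT at the time of diagnosis of MIBC". Second, the tumour must be a predominantly urothelial bladder carcinoma of at least pT2. Cystectomy, lymph node (LN) dissection and nodal biopsy are not required.

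On the reference standard, the same section states: "Pathological information (which is the gold standard) included biopsy site, date of biopsy, histology, pathological result of cystectomy and LN dissection". The list goes on to "number of LN resected, number of positive LN, necrosis, and presence of pCR after NAC", so the plan expects some specimens to be taken after NAC. It has no rule on whether a nodal biopsy counts as verification in a patient without dissection.

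The Objectives section aims at LN staging at diagnosis and adds in brackets "before and after NAC and before cystectomy and LN dissection".

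For CT and PET alike, the Statistical analysis section says only that "we will calculate the sensitivity, specificity, false positive rate, false negative rate, Youden index". It names no denominator, has no rule for patients without nodal pathology, and does not pair scans with specimens.

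The Introduction explains how imaging could influence who is operated on: "Treatment decisions are taken during a tumor board, based on the staging of local disease, LN status and distant localization".

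**The concern.** Two separate mechanisms could move the raw figures away from accuracy at diagnosis.

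**Selective verification.** Only patients with nodal pathology can be scored. If nodal or metastatic findings on PET or CT affect who has nodes removed or biopsied, the verified patients are not a random sample of those scanned. With an error-free reference, less frequent verification of PET-positive patients lowers apparent sensitivity and raises apparent specificity. More frequent verification does the reverse.

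**NAC between scan and specimen.** If a diagnostic scan correctly shows nodal disease and NAC then sterilises the nodes, the scan is scored as a false positive. A missed node that NAC sterilises is scored as a true negative. A post-NAC scan set against post-NAC pathology does not have this problem, but the plan does not keep the two comparisons apart.

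Nodal accuracy is the study's only stated objective. Without verification counts by imaging result and a split by NAC, a reader cannot tell which mechanism applied or in which direction.

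**Working it through.** The plan states no sample size or target accuracy, so there is no planned figure to reproduce. What follows is illustration.

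**Inputs**
- From the Introduction: PET sensitivity (Se) 0.57 and specificity (Sp) 0.92, from the first meta-analysis cited. Youden index = 0.57 + 0.92 − 1 = 0.49. These are taken as true here, although they may themselves come from operated patients.
- Assumed, because the documents give no values: verification probabilities v+ (PET-positive) and v− (PET-negative), nodal prevalence p = 0.25, share s of nodal disease sterilised by NAC, and NAC rates.

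**Step 1: verification only, no NAC effect**

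Se_obs = Se·v+ / [Se·v+ + (1−Se)·v−]

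Sp_obs = Sp·v− / [Sp·v− + (1−Sp)·v+]

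| v+ / v− | Se_obs | Sp_obs | Youden |
|---|---|---|---|
| 0.9 / 0.9 | 0.570 | 0.920 | 0.490 |
| 0.7 / 0.9 | 0.508 | 0.937 | 0.444 |
| 0.5 / 0.9 | 0.285/0.672 = 0.424 | 0.828/0.868 = 0.954 | 0.378 |
| 0.9 / 0.6 | 0.513/0.771 = 0.665 | 0.552/0.624 = 0.885 | 0.550 |

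Prevalence cancels out. Equal rates give no bias, and the direction depends on which group is verified more often.

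**Step 2: NAC only, diagnostic scan, everyone verified**

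Let c+ and c− be the shares of PET-positive and PET-negative nodal disease sterilised (NAC rate × s).

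- TP = p·Se·(1−c+)
- FN = p·(1−Se)·(1−c−)
- FP = (1−p)(1−Sp) + p·Se·c+
- TN = (1−p)·Sp + p·(1−Se)·c−

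NAC for all, sterilisation unrelated to the PET result (c+ = c− = s):
- s = 0.3: Sp = (0.690 + 0.03225)/0.825 = 0.875.
- s = 0.5: Sp = (0.690 + 0.05375)/0.875 = 0.850.
- Se stays 0.570 in both, because TP and FN shrink by the same factor.

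NAC use related to the PET result, s = 0.5:
- NAC in 80% of PET-positive and 30% of PET-negative patients (c+ = 0.40, c− = 0.15): Se = 0.0855/0.1769 = 0.483; Sp = 0.7061/0.8231 = 0.858.
- NAC in 30% and 80% (c+ = 0.15, c− = 0.40): Se = 0.1211/0.1856 = 0.653; Sp = 0.7330/0.8144 = 0.900.

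So unchanged sensitivity is a result of the independence assumption.

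**Step 3: both mechanisms, v+/v− = 0.5/0.9, NAC for all**

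TN is multiplied by 0.9 and FP by 0.5.
- s = 0.3: Sp = 0.6500/0.7014 = 0.927.
- s = 0.5: Sp = 0.6694/0.7350 = 0.911.
- Se = 0.424 in both.

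Here the two errors nearly cancel in specificity (93-91% against 92%) while sensitivity is well off. A Begg-Greenes correction on the PET result returns 0.570 and 0.875/0.850: it removes the verification error and leaves the NAC error. With v+/v− = 0.9/0.6, both errors lower specificity, so cancellation cannot be relied on.

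**The case against.** The strongest reply is that the objective, by referring to the period before cystectomy and dissection, already implies operated patients. The Introduction's benchmark is likewise preoperative staging. On that reading the analysis is sound and only the label is missing. Part of this stands: accuracy among verified patients is a proper target. But the phrase is neither an entry rule nor an analysis set, and the same sentence also says at diagnosis. Nor does this reading settle which scan is paired with which specimen in patients given NAC.

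A second reply is that every rate above is assumed. That stands in full. The arithmetic shows possible direction and size and does not estimate the bias in this cohort.

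Three stronger readings are tempting, and the documents do not support them:
- **That PET selects who is dissected here.** The Introduction says that treatment follows staging and that, in other studies, PET changed treatment in around 25% of cases (13.5% to 68%), mainly by confirming metastatic spread. That shows a possible route. Nothing shows that it operated in this cohort.
- **That dissection is the only possible nodal reference.** Biopsy site and histology are also collected, so a nodal biopsy might verify some undissected patients. What is missing is a rule.
- **That NAC affects only specificity, or always offsets the verification error.** Steps 2 and 3 show that both fail under equally plausible assumptions.

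**Conclusion.** The point holds as a gap in the definition of the analysis. The plan does not say whose results enter the accuracy tables, what counts as nodal verification, or how scans before and after NAC are matched to pathology. Pooled raw indices could therefore differ from accuracy at diagnosis. The documents do not establish that they will.

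In the scenarios tried, apparent sensitivity ranged from 42% to 67% around an assumed 57%, and apparent specificity from 85% to 95% around an assumed 92%, when each mechanism acted alone. If verification does not depend on imaging and no NAC comes between scan and specimen, the raw figures are unbiased. The false positive and false negative rates carry the same errors, being the complements of specificity and sensitivity.

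This should be corrected, because it affects the only stated objective and the main remedy uses data already being collected. Confidence is medium, since the actual verification and NAC rates are unknown.

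**What to change.** 1. **Define and label the accuracy set.** Make the primary set patients with nodal pathology: LN dissection, with a statement on whether a nodal biopsy counts. Label the result as accuracy among verified patients. For the diagnostic scan, report patients dissected without prior NAC separately from those given NAC. Report post-NAC scans against post-NAC pathology as a separate comparison.
2. **Show who was verified.** Tabulate verified and unverified patients by PET N and M result and by CT N and M result.
3. **Optional, if numbers allow.** Add a Begg-Greenes or inverse-probability-weighted sensitivity analysis with confidence intervals, only in strata that contain verified patients. Condition on PET and CT status for both N and M, because the Introduction links PET-driven treatment change mainly to metastatic spread. Alternatively, restrict it to imaging-M0 patients and label it so, since the plan assigns M1a "in case of metabolic activity of non-regional LN".

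**Cost.** Items 1 and 2 need a few sentences and one table, with no new patients or scans. The NAC split makes subgroups smaller and intervals wider. Item 3 assumes that verification depends only on recorded variables, and so must NAC use wherever post-NAC pathology is set aside. It can also lose precision. In 40,000 simulated cohorts of an assumed 100 patients (prevalence 25%, verification 50/90%, no NAC effect, correction on the PET result alone), the 95% sampling range for specificity was about 84-100% corrected against 90-100% raw. For sensitivity it was about 34-78% against 19-67%. Precision for the fuller correction on N and M was not calculated.

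### CT nodal status may come from medical reports with no date limit, so PET or pathology findings could enter the CT accuracy figures

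*Combined protocol and SAP*

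**What the plan says.** All the relevant text is in Patients and Methods, including its Objectives and Statistical analysis parts.

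- **CT source.** "CT data will be extracted from radiological or medical reports". A bracket adds that this covers CT before and after neoadjuvant chemotherapy (NAC). The study team then classifies the lesions described under the 8th TNM edition.
- **CT node criterion.** Under RECIST 1.1, a node counts as pathological when its smallest axis exceeds 15 mm.
- **PET source.** "FDG-PET CT results will be extracted from nuclear medicine reports for the University Hospital, or by exam reviewing for Institute Bergonie exams". General medical reports are not listed as a source for PET.
- **Design and entry.** "Patients will be retrospectively included from both the University Hospital and the Cancer Center from Bordeaux", and "patients should have undergone a FDG-PET CT at the time of diagnosis of MIBC".
- **Reference standard.** "Pathological information (which is the gold standard) included biopsy site, date of biopsy, histology, pathological result of cystectomy and LN dissection".
- **Analysis.** "For diagnosis accuracy of CT and FDG-PET CT, we will calculate" sensitivity, specificity, the two error rates and the Youden index.

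The dates listed for collection are those of birth, biopsy, relapse, and last news or death. No date of CT, CT report or PET is listed, and the text gives no surgery date. Table 1, cited for type of surgery, is not reproduced in the text available for this review. No blinding of data extractors and no re-reading of CT images is mentioned.

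**The concern.** A radiology report records what the radiologist saw on the CT. A medical report, such as a clinic letter or tumour board summary, may state the patient's stage from everything known on the day it was written. The Introduction says that treatment is decided at a tumour board on local, nodal and distant staging together, so documents that merge these sources are a plausible part of the file.

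All patients had a PET at diagnosis and data are gathered afterwards, so reports written after PET, or after cystectomy, may already be in the record at extraction. Nothing in the plan rules them out as a source for the CT call. Because neither dates nor source are recorded, an affected call could not be found or excluded later.

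Only CT has this route, so any effect would not cancel between the two modalities. At stake is whether the reported CT figures describe CT alone, and hence whether the CT and PET results, shown with the same measures, can be read next to each other.

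**Working it through.** **What the text permits.** The plan states no figure to reproduce: no sample size, CT accuracy target or planned difference. The first check is therefore of the rules themselves.

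1. Does the reference to NAC limit the report date? No. It places the CT relative to chemotherapy and does not say when the report used for extraction was written.
2. Does the 15 mm rule close the route? In part. Where the report gives the CT node size, a smaller node that is merely PET-avid would not become CT-positive. Where the report gives only a nodal category or a verbal statement, the rule cannot be applied, and the plan does not say what happens then.
3. Can the problem be detected later? Not from the listed data, for want of source and dates.

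**Illustration of direction.** Inputs:

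- Sensitivity of CT 0.40 and of PET 0.56, from the second meta-analysis in the Introduction. These are background values, not design assumptions.
- Specificity 0.92, given for PET by the first meta-analysis. It is assumed here for CT too, because the Introduction calls the specificities similar.
- *f*, the share of CT calls altered by later information. It is not in the documents, so 10% to 50% is assumed.

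Apparent CT sensitivity = (1 − *f*) × 0.40 + *f* × *s*, and gap = 0.56 minus that value. Without contamination the gap is 0.56 − 0.40 = 16 points. Three values of *s*:

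- (a) The CT call repeats the PET call: *s* = 0.56.
- (b) CT is called positive if either scan is positive, assuming conditional independence: *s* = 1 − 0.60 × 0.44 = 0.736.
- (c) The CT call repeats pathology: *s* = 1.

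| *f* | (a) CT sensitivity; gap | (b) CT sensitivity; gap | (c) CT sensitivity; gap |
|---|---|---|---|
| 10% | 41.6%; 14.4 | 43.4%; 12.6 | 46.0%; 10.0 |
| 20% | 43.2%; 12.8 | 46.7%; 9.3 | 52.0%; 4.0 |
| 30% | 44.8%; 11.2 | 50.1%; 5.9 | 58.0%; −2.0 |
| 50% | 48.0%; 8.0 | 56.8%; −0.8 | 70.0%; −14.0 |

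The gap reaches zero at *f* = 0.16/0.336 = 48% in (b) and at 0.16/0.60 = 27% in (c).

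Specificity has no single direction. At *f* = 50% it stays at 92% in (a), falls to 0.5 × 0.92 + 0.5 × 0.92² = 88.3% in (b), and rises to 0.5 × 0.92 + 0.5 × 1 = 96% in (c).

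The CT Youden index starts at 0.40 + 0.92 − 1 = 0.32. At *f* = 20% it is 0.352 in (a), 0.372 in (b) and 0.456 in (c).

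Here *f* is not the share of calls taken from medical reports. It is the smaller share in which the report post-dates PET or surgery, the 15 mm rule could not be applied, and the later finding changed the call.

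**The case against.** The strongest reply is that the plan does not tell anyone to copy a clinician's nodal category. The team classifies described lesions itself, against a size threshold ("RECIST1.1 criteria allowed to describe pathological LN (corresponding to LN with smallest axis greater than 15mm"). This is a real safeguard and narrows the concern mainly to reports without a node size. It does not remove it, because such reports have no stated handling.

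Second, nothing says that any medical report post-dates PET or surgery, and the wording can be read as a fallback when the radiology report is missing. The objective also places staging before cystectomy, so the CT call is clearly meant to be preoperative. This stands as far as it goes. A reader might infer that CT calls are in fact contaminated, or that surgical results are routinely carried back into them. The documents support neither. They show only that the plan neither prevents nor could detect it. The post-surgery route, which gives the largest figures above, is also the most speculative.

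Third, CT is not in the stated objective, and the plan sets out no test, margin or hypothesis for CT against PET. That is correct, and it limits the weight of the point. The CT accuracy measures are nevertheless an explicit planned output.

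**Conclusion.** The concern holds in a limited form. As written, the source rule can admit CT calls informed by PET or pathology, chiefly where no node size is given. This would bias the CT sensitivity, specificity and Youden index. Sensitivity would most likely rise and the descriptive gap to PET would shrink.

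The size cannot be estimated from the documents. The table shows what would follow from assumed shares and background accuracy values, not what is likely in this cohort.

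Two stronger readings should be resisted. One is that the PET accuracy result is compromised: it is not affected, because PET calls come from nuclear medicine reports or exam review. The other is that a formal comparison of CT with PET is invalidated: the plan makes none. This is a worthwhile correction to a secondary, descriptive output.

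**What to change.** Replace the CT source rule with text such as:

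> CT N status will be taken from the original radiology report of the CT at each time point (before or after NAC). A medical report will be used only if the radiology report is unavailable and the medical report is dated before the PET at the same time point and before surgery. The source of the CT call and the dates of CT, CT report, PET and surgery will be recorded. CT accuracy will be repeated in a sensitivity analysis limited to patients whose radiology report pre-dates the corresponding PET, with PET accuracy shown for the same patients.

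The date limit is tied to the PET at the same time point because a report on a post-NAC CT cannot pre-date the diagnostic PET. The sensitivity analysis is needed because a radiology report can itself be written with PET known. It also leaves patients whose radiology report came after PET in the main CT analysis.

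The cost is a few extraction fields and a smaller sample for the CT figures, by a number that the documents do not allow to be estimated. Some influence may remain, since a post-NAC CT may be read with the diagnostic PET on file. Only a CT re-read blinded to PET and pathology would remove that, at greater cost.

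### The nodal accuracy analysis does not say which scan is scored against which pathology, nor separate patients by NAC; baseline scans scored against post-NAC dissection would misstate accuracy at diagnosis

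*Combined protocol and SAP*

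**What the plan says.** The Introduction states the aim: "We aimed to investigate the role of FDG-PET CT and its accuracy in LN staging of MIBC at diagnosis". The Objectives section widens the time frame within one sentence, to "LN staging at the diagnosis of MIBC (before and after NAC and before cystectomy and LN dissection".

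Patients and Methods supplies the data behind this objective:

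- **Baseline PET.** It is an entry condition: "patients should have undergone a FDG-PET CT at the time of diagnosis of MIBC". NAC is not an exclusion.
- **CT.** "CT data will be extracted from radiological or medical reports (before and after NAC".
- **Repeat PET.** It is conditional, "If patients undergo a FDG-PET CT before and after NAC", and its only stated use is to record a metabolic response category.
- **Reference.** "Pathological information (which is the gold standard) included biopsy site, date of biopsy, histology, pathological result of cystectomy and LN dissection". The surgical items include "number of LN resected, number of positive LN, necrosis, and presence of pCR after NAC", so some of this pathology is post-treatment.

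The Statistical analysis section lists, once for CT and PET together, "sensitivity, specificity, false positive rate, false negative rate, Youden index". It names no scan, reference, time point or NAC group.

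**The concern.** A diagnostic 2×2 table is interpretable only if the test and the reference describe the same disease state. A PET at diagnosis and a dissection after chemotherapy do not, if the chemotherapy has changed the nodes in between. The plan records pathological complete response after NAC, so response is anticipated, although it does not say how often nodes are cleared.

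The text permits at least three analyses:

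1. Baseline scan against dissection in all operated patients. For NAC patients the reference is then a later, treated state.
2. Post-NAC scan against post-NAC dissection. The states match, but the result is not accuracy at diagnosis.
3. Each time point separately, with the at-diagnosis result taken only from patients operated on without NAC.

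These answer different questions and can give different numbers. In a retrospective study with no stated rule, the choice could be made after results are seen. At stake is the quantity named in the objective.

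**Working it through.** The plan gives no sample size, target accuracy or expected result, so there is no figure of its own to reproduce. The check is 2×2 algebra at patient level for analysis 1.

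**Inputs from the Introduction.** Sensitivity Se = 0.57 and specificity Sp = 0.92, from the first cited meta-analysis; ranges across studies are Se 29–81% and Sp 86.7–97%. They are used here as illustrative true values at baseline.

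**Assumed, not in the documents.** Node-positive prevalence p; NAC share f1 in scan-positive and f0 in scan-negative patients; nodal clearance k1 and k0 in scan-positive and scan-negative node-positive patients. Write m1 = f1·k1 and m0 = f0·k0.

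**Apparent cells against dissection**

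- TP′ = p·Se·(1 − m1)
- FN′ = p·(1 − Se)·(1 − m0)
- FP′ = (1 − p)(1 − Sp) + p·Se·m1
- TN′ = (1 − p)·Sp + p·(1 − Se)·m0

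With p = 0.30 and no NAC: TP 0.171, FN 0.129, FP 0.056, TN 0.644; Youden 0.490.

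**Clearance unrelated to the scan, k = 0.4.** Sensitivity stays at 57%.

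| NAC share | FP′ | TN′ | Specificity | Youden |
|---|---|---|---|---|
| 25% | 0.0731 | 0.6569 | 90.0% | 0.470 |
| 50% | 0.0902 | 0.6698 | 88.1% | 0.451 |
| 100% | 0.1244 | 0.6956 | 84.8% | 0.418 |

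At 50%, 0.0902 − 0.056 = 0.0342, so per 100 patients 3.4 of 9.0 apparent false positives are cleared nodes, and the false positive rate goes from 8.0% to 11.9%. With half on NAC, over p = 20–40% and k = 20–50%, specificity is 85.0–90.8%.

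The loss in specificity is J·p·m/(1 − p + p·m), with J the true Youden index and m the common value of m1 and m0. Over the Introduction's PET ranges J runs from 0.29 + 0.867 − 1 = 0.157 to 0.81 + 0.97 − 1 = 0.780. With p = 0.3, k = 0.4 and half on NAC (m = 0.2), the loss is 1.2–6.2 points.

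**Clearance related to the scan, half on NAC, p = 0.30**

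- k1 = 0.5, k0 = 0.3: Se 0.12825/0.2379 = 53.9%, Sp 0.66335/0.7621 = 87.0%, Youden 0.410.
- k1 = 0.3, k0 = 0.5: Se 0.14535/0.2421 = 60.0%, Sp 0.67625/0.7579 = 89.2%, Youden 0.493.

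Sensitivity and Youden therefore have no fixed direction. Specificity falls unless m0/m1 exceeds the diagnostic odds ratio Se·Sp/[(1 − Se)(1 − Sp)]: 0.57 × 0.92/(0.43 × 0.08) = 15.2, or 2.7 at the lowest quoted Se and Sp.

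**Does restricting to patients without NAC recover the truth?** Only if NAC use is unrelated to the scan and to nodal status. If it depends on the scan (p = 0.30, k = 0.4):

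| NAC in PET+ / PET− | No-NAC patients only: Se, Sp, Youden | All pooled: Se, Sp, Youden |
|---|---|---|
| 60% / 40% | 46.9%, 94.5%, 0.414 | 54.5%, 87.3%, 0.418 |
| 40% / 60% | 66.5%, 88.5%, 0.550 | 59.4%, 89.0%, 0.484 |
| 50% / 50% | 57.0%, 92.0%, 0.490 | 57.0%, 88.1%, 0.451 |

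In the second row the pooled figures are closer to the truth on all three measures. Over both unequal splits, p = 20/30/40% and k = 20/30/40/50%, pooling is closer on Youden in 21 of 24 cells.

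**Reweighting, first row.** Node-positive shares in the no-NAC group are 0.0684/(0.0684 + 0.0224) = 0.753 if scan-positive and 0.0774/(0.0774 + 0.3864) = 0.167 if scan-negative. In all patients 0.171 + 0.056 = 0.227 are scan-positive. Then TP = 0.227 × 0.753 = 0.171 and FN = 0.773 × 0.167 = 0.129, which returns Se 57% and hence Sp 92%. This works because NAC depends on the scan alone in the example.

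**The case against.** The plan is not silent on timing. The objective names the time points and places the scans before dissection, CT is labelled before and after NAC, and repeat PET is handled separately. Analysis by time point is a natural reading. That answers only part of the concern: an analysis of baseline scans still scores NAC patients against treated nodes unless they are kept out, and the plan does not say so.

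The strongest objection is to the obvious remedy. Patients operated on without NAC are a selected group. The Introduction says treatment decisions rest on local stage, nodal status and distant disease, so NAC use unrelated to the scan is the least supported case. As shown above, restriction can be further from the truth than pooling. This stands, and it shapes the fix.

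Two further points also stand. Every size is conditional on assumed inputs, and 57%/92% are reported preoperative results from cohorts whose NAC status cannot be checked here. And the biopsy items listed under the gold standard may simply document the bladder diagnosis. A reader might infer that biopsy and dissection are being mixed as nodal references, but the text does not establish that.

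**Conclusion.** The point holds as a gap in the analysis plan. Accuracy at diagnosis is the aim, NAC patients are eligible, dissection pathology is the nodal reference, and one unstratified set of measures is planned. Any scoring of baseline scans against post-NAC dissection would misclassify cleared nodes. Specificity would be understated except under very lopsided clearance; sensitivity and Youden could go either way. With 30% node-positive, 40% clearance and half on NAC, all assumed, the cost is about 4 points of specificity (92% to 88.1%) and 0.039 of Youden (0.490 to 0.451). The real size cannot be set from the documents.

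Two stronger inferences are not supported. A reader might conclude that the study will score baseline scans against post-NAC dissection; the plan never says this, only fails to rule it out. A reader might also conclude that the no-NAC subgroup gives the correct accuracy at diagnosis for all patients; it does so only if selection for NAC is unrelated to scan and nodal status. This is a cheap improvement to the plan, not proof of a biased result.

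**What to change.** In Objectives and Statistical analysis, name the index scan and the reference for each accuracy table, and report by NAC status without pooling:

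- **(i)** Baseline PET and CT against dissection in patients operated on without NAC, labelled as accuracy in that group.
- **(ii)** Post-NAC PET and CT against post-NAC dissection in NAC patients.
- **(iii)** Baseline scan against post-NAC dissection as a labelled descriptive table, not as accuracy at diagnosis.

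Beside (i), tabulate baseline PET and CT nodal results by NAC status, and show (i) reweighted to the baseline scan distribution of all patients. State the reweighting assumption: given the scan result, NAC use and having a dissection are unrelated to nodal status. Say also that it is doubtful, because local stage enters treatment decisions too.

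The cost is mainly wording and stratified tables. Chemotherapy regimen, the before/after-NAC labels and biopsy date are already listed for collection. Scan and surgery dates are not listed and may have to be added at both centres. The downsides are smaller groups, wider intervals, a possibly small table (ii) because post-NAC PET is conditional, and selection that reweighting may not remove.
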